1.3 Data Pooling

The issue of poolability of the data entails two features: the combining of data across study sites and the method of computation of an overall estimate for study endpoints. The justification for combining of data across sites is based on the clinical assessment provided by Meinert (1986): the clinical study will be conducted under a common protocol for each investigational site, the study sites will be monitored for protocol compliance, the same data gathering instrument and method will be used in every site, all clinical events will be adjudicated by a common Clinical Events Adjudicator, and a Core Lab will provide the effectiveness analysis.

A test of homogeneity within US or OUS sites will be done to determine if the study sites within a location have reasonably homogeneous responses. If the responses are not homogeneous, a logistic regression analysis will be done to determine if the lack of homogeneity is due to the site or a possible imbalance in baseline characteristics of the subjects or aneurysms within a study site. If the site effect is no longer significant at $P < 0.10$ after adding the potentially unbalanced baseline covariates then it will not be considered a source of lack of homogeneity.

If the above analysis indicates that study site responses are homogeneous, an analysis of the homogeneity across US or OUS sites in aggregate will be done. A logistic regression analysis of the primary effectiveness endpoint be done and will include a covariate for US or OUS sites. This will determine if the OUS sites have a performance difference after adjustment for rupture status or other baseline subject or rupture characteristics that differ in by location in the

comparability analyses described below. If the P-value of location (US or OUS) has a P-value <0.10 after adjustment, it will be deemed to have a difference in response by location and the analysis will be done by stratifying the study sites by location and performing an analysis adjusting for the location.

In study sites with small numbers of subjects, it will be difficult to evaluate a site by treatment interaction. For this reason, study sites with fewer than 6 subjects will be combined into pseudosites. Pseudosites will be used for all multivariate analyses including the analysis to determine a site by treatment interaction for pooling.

Since the study has only one group, it is not possible to do a treatment comparison by logistic regression to account for any study site effects or location difference. Instead, the sites or locations (whichever retains non-homogeneity) will be grouped into subgroups with similar responses these will be combined to get an overall treatment effect by the method of Fleiss. This will result is a z-statistic test provided in the analysis section below.

1.4 Multiplicity

Since there is only one hypothesis tested for effectiveness, there is no inflation to alpha and no multiplicity adjustment is needed.

1.5 Missing Data

Subjects whose data are not missing at random, such as those who exit the study due to a device-related primary safety event will be imputed as a safety and effectiveness failure. These subjects are not missing at random. Subjects who are absent at twelve months and missing at random will have their success or failure imputed for the primary effectiveness endpoint by multiple imputations with random selection from subjects with outcomes with similar aneurysm locations, rupture status and if indicated, aneurysm size or geographic location, followed by sensitivity analyses.

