1.2 Analysis Populations

The subject populations represented in the final analyses will be determined after CEA adjudication of all AEs and Protocol Deviations. The analysis populations include:

- The intent to treat (ITT) population includes every study subject in whom there is an attempt to place the WEB device. The primary safety and effectiveness analyses will be performed on this population.
- The completed cases (CC) population includes the group of subjects who complete the 12 month visit. Supportive analyses of the primary safety and effectiveness endpoints will be completed with this population.
- The per-protocol (PP) population includes all CC cases who additionally meet all study eligibility criteria, have available study data for the study endpoint and do not have a major protocol violation that affects primary safety or effectiveness. Selected sensitivity analyses will be done with the PP population.

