1.9 Justification for Safety Threshold

The WEB device was designed for the treatment of WNBAs. No prospective clinical trial has focused specifically on the rates of major stroke or death in patients with WNBAs. Therefore, the observed safety failure rate in this study will be compared with a performance goal (Objective Performance Characteristic (OPC)) of 0.28. This performance goal was derived from the rates of primary safety events reported in the clinical literature for other endovascular or neurosurgical methods of treatment of bifurcation and wide neck IAs which was 0.1993. The OPC represents the upper two-sided confidence limit on this rate. The WEB-IT safety outcome will be considered a success if the safety failure rate observed in this study is statistically significantly less than 28%.

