1.10 Sample Size Calculations

The sample size for the primary effectiveness endpoint for this single arm study is computed using Pass 2008 software for a single binomial proportion. If the effectiveness rate in the WEB group is expected to be 0.323 with core laboratory adjudication, then 80% power is achieved with a one-sided alpha of

0.05 with 84 evaluable subjects. This sample size has been adjusted upward to 95 based on statistical simulations in which all five seeds had to have power of at least 80%. Assuming a loss to follow-up of about 15% in this critically ill population, the recruited sample size will be $95/0.85 = 111.8$ or 112 subjects. The planned analysis is anticipated to take place when the requisite number of evaluable subjects has completed the 12 month follow-up visit.

Pass 2008 was also used to estimate the sample size for the primary safety endpoint. To have 80% power to detect a difference between an expected observed primary safety event rate (as defined for this population above) of 0.147 and the OPC = 0.28, the sample size is 62 subjects. The sample size for effectiveness is larger and thus 112 will be the sample size for the study.

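### SAP 1.5 gives no rule in the primary safety analysis for subjects lost at random without an event; a literal ITT proportion would count them as event-free and favour the device

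*SAP*

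**What the plan says.** SAP 1.5 has two rules.

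- The first is for informative loss, where the missing-at-random assumption fails. It gives an example and the handling: "such as those who exit the study due to a device-related primary safety event will be imputed as a safety and effectiveness failure".
- The second is for subjects with no twelve-month result whose loss is taken to be at random. They "will have their success or failure imputed for the primary effectiveness endpoint by multiple imputations", drawing on subjects with similar location, rupture status and, if indicated, size or geography, "followed by sensitivity analyses". Safety is not named in this second rule.

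SAP 1.2 defines ITT as every subject with an attempted placement and adds: "The primary safety and effectiveness analyses will be performed on this population". Of the completed-cases set, those who complete the 12-month visit, it says: "Supportive analyses of the primary safety and effectiveness endpoints will be completed with this population".

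The safety endpoint (Protocol, Primary Endpoints) counts nonaccidental death or major stroke to day 30, then major ipsilateral stroke or neurologic death to one year. SAP 1.9 calls safety a success "if the safety failure rate observed in this study is statistically significantly less than 28" per cent, and 1.7 requires both primary endpoints to be met. SAP 1.10 sizes the study "Assuming a loss to follow-up of about 15% in this critically ill population". The Kaplan-Meier analyses in 1.12 are additional safety analyses, and none is of the primary composite.

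**The concern.** The first rule in 1.5 adds little for safety in the example it gives: a subject who exits because of a primary safety event is already a failure under the endpoint definition. The subjects who need a rule are those who leave without a recorded event. For effectiveness they are imputed. For safety the supplied text is silent.

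A proportion on ITT as defined has every attempted subject in the denominator and recorded events in the numerator. Unless something more is said, unobserved follow-up then counts as event-free follow-up. That lowers the observed event rate on an endpoint where low is good and which study success requires. Leaving these subjects out is the obvious alternative, but then the analysis set is no longer the ITT set of 1.2. In an open single-arm study, a rule left unwritten could be settled after the events are known.

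The completed-cases analysis does not help. Read literally, it drops subjects who died before the 12-month visit, and many of those deaths are primary safety failures. The per-protocol set is a subset of completed cases and has the same defect.

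**Working it through.** **Inputs.** Null rate 0.28 (SAP 1.6, 1.9); expected rate 0.147, N = 112 and 15% loss (1.10). One-sided alpha 0.05 is stated for effectiveness and assumed for safety.

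**The plan's own figure.** SAP 1.10 gives, for an expected rate "of 0.147 and the OPC = 0.28, the sample size is 62 subjects". With an exact one-sided binomial test at 0.05, the smallest n with at least 80% power is 62: pass at 11 or fewer events, P(X ≤ 11 | 62, 0.28) = 0.044, P(X ≤ 11 | 62, 0.147) = 0.807. The stated figure reproduces, which supports the assumed alpha.

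**The test at N = 112.** Pass at 23 or fewer events: P(X ≤ 23 | 112, 0.28) = 0.046. Power at 0.147 is 0.965.

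**Reading A: lost subjects stay in as event-free.** Let d be the share lost and L the share of events after day 30 (not in the documents; 25% to 75% assumed). If loss is spread evenly over the year, about half of the lost subjects' late events go unseen:

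apparent rate = 0.28 × (1 − d × L × 0.5); false-pass rate = P(X ≤ 23 | 112, apparent rate).

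| d | L | Apparent rate | False pass |
|---|---|---|---|
| 15% | 25% | 0.28 × 0.98125 = 0.2747 | 5.9% |
| 15% | 50% | 0.28 × 0.9625 = 0.2695 | 7.5% |
| 15% | 75% | 0.28 × 0.94375 = 0.2643 | 9.3% |
| 5% | 25% | 0.28 × 0.99375 = 0.2783 | 5.0% |
| 5% | 75% | 0.28 × 0.98125 = 0.2747 | 5.9% |

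If all 15% were lost just after day 30, the factor 0.5 drops out and the false-pass rate is 7.5%, 11.6% or 17.2% for L = 25%, 50% or 75%. If nothing at all were observed on the lost subjects, the apparent rate is 0.28 × 0.85 = 0.238 and the false-pass rate is 24.5%. That is a theoretical bound for loss unrelated to outcome.

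**Reading B: lost subjects are left out.** 112 × 0.85 ≈ 95 remain. Pass at 19 or fewer: P(X ≤ 19 | 95, 0.28) = 0.049; power at 0.147 is 0.941. The level holds if loss is unrelated to outcome.

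**Where the readings disagree.** Suppose 95 subjects are fully observed and the other 17 contribute no events. Then 20 to 23 events pass under A (23 or fewer of 112) and fail under B (19 or fewer of 95). At a true rate of 0.28, P(20 ≤ X ≤ 23 | 95) = 0.193. This uses the same extreme as the 24.5% bound, with no events seen on the lost subjects, so 19% is towards the high end.

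**The case against.** A reader might infer that the plan counts lost subjects as event-free and that the safety test is therefore biased. The documents do not say so. SAP 1.2 gives no denominator rule for unknown 12-month status, and 1.10 speaks of evaluable subjects and times the analysis by completed 12-month visits. Leaving out unknowns is a reasonable reading, and under it there is no inflation when loss is unrelated to outcome. This stands: event-free counting follows from the literal ITT definition but is not a stated rule.

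Nor is it right that 1.5 imputes for effectiveness only. Its first rule makes subjects not missing at random safety failures, and the device-related exit is given as an example of that class. The most dangerous kind of loss is therefore addressed, though the class is loosely defined. The gap concerns subjects missing at random.

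The 15% is used to inflate the effectiveness sample, whose endpoint needs 12-month imaging. Safety status is easier to obtain: the Schedule of Assessments collects adverse events at every visit from the procedure on, so a subject without an angiogram may still have known status. At 5% loss spread over the year the effect nearly vanishes. The 24.5% bound is not realistic either, since every ITT subject had an attempted placement and procedural events would be seen.

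Finally, the silence is judged on incomplete text: part of the SAP is not in the supplied copy, and the protocol is a synopsis. These points limit the size and certainty of the effect. None of them supplies the missing rule.

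**Conclusion.** The point holds as a gap in specification with a conditional bias. In the supplied text, subjects lost at random without an event have no stated handling in the co-primary safety analysis. Under a literal ITT proportion the test would favour the device: 4.6% becomes about 6% to 9% at 15% loss spread over the year, or 5.0% to 5.9% at 5% loss. If they are excluded and loss is unrelated to outcome, the level is 4.9% with 94% power, but the set is no longer ITT as 1.2 defines it.

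The figures rest on the assumed safety alpha, the assumed share of late events and the assumed loss patterns. A claim that the safety test is biased as planned would go beyond the documents. At the expected rate of 0.147 power is high on either reading (97% or 94%), so the choice matters when safety is marginal, which is when the test has to protect. The plan should be corrected before the data are analysed.

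**What to change.** Extend SAP 1.5 to the primary safety endpoint:

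1. Multiply impute 12-month safety status for subjects lost without a primary safety event, conditional on being event-free to the date of loss and with the same covariates as for effectiveness.
2. Treat non-neurologic deaths after day 30 as known non-events, not as missing. In any time-to-event sensitivity analysis treat them as competing events; censoring them in a Kaplan-Meier analysis estimates a different quantity from the proportion tested against 0.28.
3. In the completed-cases safety analysis, keep every subject with a primary safety event, whether or not the 12-month visit was reached.
4. Add a tipping-point analysis: how many lost subjects would have to be failures for the test to fail. For illustration, at the expected rate 95 observed subjects give 0.147 × 95 ≈ 14 events; failure begins at 24, so 24 − 14 = 10 of the 17 lost would have to be failures.

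Counting every lost subject as a failure is not a workable primary rule: it leaves 23 − 17 = 6 events among 95 observed subjects, with power of about 1% at 0.147.

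The cost is SAP wording and minor programming, with no new data. The safety estimate may become slightly less favourable than under event-free counting.

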Primary Endpoints:	
The study's primary effectiveness endpoint is the proportion of subjects with complete aneurysm occlusion without retreatment, recurrent subarachnoid hemorrhage, without significant parent artery stenosis (>50% stenosis) at one year after treatment. A subject will be considered an effectiveness success upon meeting all of the above criteria.
 
The study's primary safety endpoint is the proportion of subjects with death of any nonaccidental cause or any major stroke (defined as an ischemic or hemorrhagic stroke resulting in an increase of 4 points or more on the National Institutes of Health Stroke Scale) within the first 30 days after treatment or major ipsilateral stroke or death due to neurologic cause from day 31 to the 1 year after treatment. A subject will be considered a safety failure upon meeting any of the above criteria. All safety events will be adjudicated by an independent clinical events adjudicator.
 
The study will be interpreted as a success if both of the primary effectiveness and primary safety endpoints are met.

CLINICAL PROTOCOL SYNOPSIS

Secondary Endpoint:	The study's secondary endpoint is the proportion of subjects with angiographic aneurysmal recurrence defined as aneurysm growth or recanalization at one year after treatment.
Other Endpoints:	
Secondary analyses include:
 
 • Technical success • IA occlusion status at other time points (6 mo, 2, 5 yrs) • Change in mRS (for unruptured subjects only) • % Aneurysm occlusion • Proportion of IAs with each occlusion category at all angiographic follow-up time points. • Durability of occlusion – defined as “Same”, “Better”, “Worse” when comparing the 1 year angiographic result with the 6 month angiographic result

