Schedule of Examinations:	Screening (Day -30 to Day 0) Procedure

CLINICAL PROTOCOL SYNOPSIS

	Discharge 30-day follow-up (mRS per office or telephone update) Six month follow-up (office visit and angiographic follow-up) One year follow-up (office visit and angiographic follow-up) Two year and four year follow-up (office visit per standard of care or telephone update) Three year and five year follow-up (office visit and imaging follow-up per standard of care)
--	---

Figure 1. Diagram of Study Flow.

CLINICAL PROTOCOL SYNOPSIS

Table 1. Schedule of Assessments.

Parameter	Screening	Procedure	Discharge	30-Day Follow-Up	6-Month Follow-Up	1-Year Follow-Up	2- and 4-Year Follow-Up	3- and 5-year Follow-Up
Health history	X							
Physical examination	X	X	X		X	X		X
Neurological examination	X				X	X		X
Site and subject information	X							
Aneurysm information (size, location, etc.)	X	X						
Rupture status	X							
Hunt and Hess Grade (ruptured aneurysms only)	X							
Microcatheter(s) used		X						
Ancillary devices used (eg, stent, balloon used)		X						
Medications used	X	X	X		X	X		X
Size and lot number of WEB device(s) used		X						
WEB procedure fluoroscopy time		X						
Total procedure fluoroscopy time		X						
3D angiographic imaging	X	X			X	X	Optional	X*
Additional imaging per standard of care							X	X
Occlusion assessments (Core Lab)			X		X	X	Optional	X*
Modified Rankin Scale score	X		X	X	X	X		
NIHSS score	X	As required						
QOL Assessment (EQ-5D)					X			
Additional scales as appropriate		X			X	X	Optional	Optional
Technical events		X						
Adverse events		X	X	X	X	X	X	X
Retreatments /Additional Procedures				X	X	X	X	X
Rebleed (if ruptured)/New bleed			X	X	X	X	X	X
Comments	X	X	X	X	X	X	X	X

* Per local Standard of Care

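### The imputation of missing 12-month effectiveness outcomes ignores each subject's own 6-month Core Lab occlusion result

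*SAP*

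**What the plan says.** SAP 1.5 divides subjects without a 12-month outcome into two groups. Those whose loss is not random, for example after a device-related primary safety event, are counted as failures. For the others, "Subjects who are absent at twelve months and missing at random", success or failure on the primary effectiveness endpoint is multiply imputed by "random selection from subjects with outcomes with similar aneurysm locations, rupture status and if indicated, aneurysm size or geographic location". Sensitivity analyses are to follow, but their content is not given.

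The protocol collects a closely related earlier measurement. The Schedule of Examinations has an angiographic visit at six months, and Table 1 marks a Core Lab occlusion assessment at that visit. Other Endpoints lists 6-month occlusion status as an analysis. It also defines durability "when comparing the 1 year angiographic result with the 6 month angiographic result".

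On the intent-to-treat population, SAP 1.2 states: "The primary safety and effectiveness analyses will be performed on this population". The completed-cases population "includes the group of subjects who complete the 12 month visit", and the per-protocol population is a subset of it.

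**The concern.** Missing at random is an assumption made conditionally on the variables in the imputation. Here it amounts to saying that, once location and rupture status are known (and size or geography where used), loss tells us nothing about the outcome. The 6-month reading is an earlier look at the main component of the primary endpoint, and many lost subjects may have one. If it predicts the 12-month result and is also related to who is lost, leaving it out biases the primary estimate.

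The bias could produce a false claim of effectiveness or sink a trial of an effective device. The completed-cases and per-protocol analyses cannot show it, because both drop the same lost subjects.

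**Working it through.** **The plan's figures.** SAP 1.10 uses 0.323 against 0.203 at one-sided 0.05 with 80% power. The exact binomial test gives 84 as the smallest sufficient number (success at 24 or more; alpha 0.0442, power 0.8005), which reproduces the plan. The recruited number also follows: 95/0.85 = 111.8, so 112.

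**How much is imputed.** 112 − 95 = 17 subjects, and 17/112 = 15.2%. With 0.323 observed among 95, the overall rate is 95 × 0.323/112 = 0.274 if all 17 fail and (95 × 0.323 + 17)/112 = 0.426 if all succeed.

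**Assumptions.** The documents give neither the loss pattern nor the 6-to-12-month agreement, so these inputs are mine:
- 12-month success is 85.5% if occluded at 6 months and 4% if not.
- For a true rate of 20.3%, 20% are occluded at 6 months: 0.20 × 0.855 + 0.80 × 0.04 = 0.203.
- For the planned 32.3%, 34.7% are occluded at 6 months.
- There are four equally likely locations and 20% are ruptured, both unrelated to 6-month status.
- Every lost subject has a 6-month result and goes to the donor rule.

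**Size of the bias by hand.** The plan's rule in effect gives lost subjects the completers' rate. Suppose 5% of occluded and 17.5% of non-occluded subjects are lost:
- Overall loss is 0.20 × 0.05 + 0.80 × 0.175 = 0.15.
- The occluded share of completers is 0.20 × 0.95/0.85 = 0.2235.
- The expected estimate is 0.2235 × 0.855 + 0.7765 × 0.04 = 0.222, against a true 0.203.

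With 25% and 12.5% lost, the occluded share is 0.20 × 0.75/0.85 = 0.1765 and the estimate is 0.1765 × 0.855 + 0.8235 × 0.04 = 0.184.

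**Effect on the decision.** With N = 112, success requires at least 31 (exact alpha 0.0377; power 0.875 at 0.323, both with complete data). I simulated 24,000 trials per case with 20 imputations each, declaring success when the pooled mean times N reached 31. Paired entries are for matching on 6-month status / a logistic model that includes it.

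| Loss: occluded vs not | Mean, plan's rule (true 20.3%) | False success, plan's rule | False success, 6-month status used | Chance of success at 32.3%, plan's rule | Same, 6-month status used |
|---|---|---|---|---|---|
| 15% vs 15% | 20.3% | 4.3% | 3.6 / 3.7% | 82.9% | 84.5 / 84.7% |
| 10% vs 16.25% | 21.2% | 6.7% | 3.1 / 3.5% | 89.3% | 85.0 / 85.8% |
| 5% vs 17.5% | 22.2% | 10.8% | 3.4 / 4.0% | 93.8% | 85.3 / 86.3% |
| 20% vs 13.75% | 19.3% | 2.5% | 3.6 / 3.5% | 74.9% | 84.5 / 84.1% |
| 25% vs 12.5% | 18.4% | 1.4% | 3.7 / 3.5% | 64.4% | 84.1 / 83.1% |

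Overall loss is 15% in every case at 20.3%, and 13.2–16.8% at 32.3%.

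**Varying the assumptions** (false success under the plan's rule at 5% vs 17.5% loss, then at 25% vs 12.5%):
- Weaker agreement (70% vs 7.9%): 8.9% and 1.9%; with 6-month status, 3.6–4.3%.
- N = 150, the protocol maximum, success at 40 or more: 11.7% and 1.2%; with 6-month status, 3.3–3.8%.
- 50% ruptured: 10.9% and 1.4%; with 6-month status, 3.3–3.9%.
- Pooled z-test with Rubin's variance: 10.0% and 1.2%; with 6-month status, 3.5–4.3% across all five loss patterns.

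A separate simulation assumed 25% occluded and 70% agreement, with a z-test. It gave 0.7–16.8% false success under the plan's rule and 4.9–5.8% with 6-month status.

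**The case against.** The strongest reply is that the illustration sends every lost subject to the donor rule, whereas SAP 1.5 counts non-random losses as failures and its wording leaves that class open. Retreatment or a further bleed before a missed visit is arguably a known failure too. If 25% of the lost non-occluded subjects (about 4 people) were counted as failures, false success at 5% vs 17.5% loss would fall to about 7%; at 50% (about 8 people) it would fall to 4.5%. This stands as a limit on the 10.8% figure. It does not answer the point: such a rule offsets the bias only by chance, and it lowers the estimate further where occluded subjects are lost more often.

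It is also fair that no bias has been shown, only the possibility of one, and that two of the four unequal loss patterns make false success less likely. Those two are the ones that cost power. The unspecified sensitivity analyses might use the 6-month result, but nothing in the text says so. Treating location and rupture as unrelated to outcome probably favours the concern modestly, since SAP 1.8 adjusts the performance goal for both.

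**Conclusion.** The concern holds for subjects classed as missing at random. The plan collects and analyses the 6-month Core Lab result but, in the SAP text available, does not use it where it would help the primary analysis most. That is a matter of text and needs no assumption. The size does: it depends on how strongly loss is tied to 6-month status, how well that status predicts the 12-month outcome, and how many lost subjects have a 6-month reading. Under the assumed inputs the estimate moves by about two percentage points either way, enough to more than double the nominal 5% error or to cut the chance of success by about 20 points (64.4% against 83–84%). If loss is unrelated to 6-month status, the bias is zero. This should be fixed, with medium confidence about how much it matters in practice. The planned numbers 84, 95 and 112 are unaffected.

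**What to change.** In SAP 1.5, add 6-month Core Lab occlusion status, where available, to the imputation alongside location and rupture status. Either of two forms works:

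1. Keep random selection, match on all three, and when a cell has fewer than 5 donors drop location first, then rupture status, always keeping 6-month status.
2. Use a logistic imputation model with the three variables and a weak penalty against separation.

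Do not insist on exact three-way matching. With four locations and two rupture states, 67–81% of lost occluded subjects would have fewer than 5 donors in the 20.3% illustration. Subjects lost before 6 months are imputed on the baseline variables alone. The wording should be settled before results are reviewed.

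The cost is SAP text and slightly more analysis; no visit, sample size or threshold changes. The reported success rate may move up or down. The logistic form leaves a small shift (mean 20.2–20.6% against 20.3%), and the collapsing match leaves almost none. With loss unrelated to 6-month status, the gain is only a little precision (chance of success 82.9% to about 84.5%). If half the lost subjects have no 6-month result, the benefit is partial: 10.8% falls to 6.3–6.9%, 1.4% rises to 2.2–2.3%, and the 64.4% chance of success rises to about 76%.
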